10.2. Sample Size Determination

10.2.1. Sample Size Assumptions

The sample size of this study has been primarily determined in order to achieve sufficient power for the principal secondary endpoint SF-36 vitality sub-score, since the anticipated effect size of this endpoint is less than that for the primary endpoint.

Approximately 600 participants are planned to be randomized (300 per arm) to receive daprodustat or placebo, who will be treated to achieve and maintain Hgb between 11 and 12 g/dL. Under the assumption that up to 10% of participants will withdraw from the study before Week 24 (start of EP), 600 randomized participants will result in at least 540 evaluable participants.

For the primary endpoint, the expected difference in mean Hgb change from baseline and the EP, between arms, is 1.0 g/dL and the anticipated between participant standard deviation (SD) is 1.5 g/dL, based on historical rhEPO trials and daprodustat clinical trial experience to date. The planned study size provides more than 99% power for superiority. In addition, it is anticipated that the smallest difference in mean Hgb change between arms that would meet the statistical criterion for superiority would be 0.25 g/dL.

For the first principal secondary endpoint of % of participants having a Hgb increase of ≥ 1.0 g/dL from baseline to EP, 540 evaluable participants provides $>90\%$ power to detect a 20% difference between daprodustat and placebo, assuming 30% of placebo arm participants will have a Hgb increase of ≥ 1.0 g/dL. In that case the smallest difference between daprodustat and placebo that would meet the statistical criterion for superiority would be 8%.

For the second principal secondary endpoint of mean change in SF-36 vitality sub-score between baseline and week 28, 540 evaluable participants provides for 79% power to detect a difference between arms under the assumption of a between treatment effect of 5 points in favor of daprodustat and a within-group standard deviation of 21 points. Prior research has determined that anemia is associated with a difference of 5.4 points from baseline for SF-36 vitality scores (Bjorner, 2007). It is expected that the smallest difference between arms that would meet the statistical criterion for superiority in this principal secondary endpoint is 3.5 points.

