- Subjects with scheduled off-treatment SF-36 data will be imputed assuming they were on treatment.
 - The low and high cutoffs at SF-36 values of 0 and 100 for traditional scoring and 22.89 and 70.42 for norm-based scoring will be applied to all imputed SF-36 values.
 - For the SF-36 principle secondary endpoint supportive analysis imputing subjects who have remote/over the phone SF-36 visits during Week 28 and those subjects who were treatment interrupted prior to their Week 28 visit will be performed using on treatment SF-36 values and conducted under a set of assumptions about missing sf-36 values (see Section 10.6.3). This is a similar imputation strategy as outlined above but will be based on on-treatment SF-36 values and consider those subjects who completed SF-36 remotely/over the phone or who were treatment interrupted prior to Week 28 as missing.

Supportive Analyses

- For the first principal secondary endpoint, a supportive analysis using while alive and on treatment strategy (on-drug analysis) will be performed using a Cochran-Mantel-Haenszel (CMH) chi-squared test, adjusting for treatment, and region (see Section 5.3), will be used to make comparisons between the treatment groups. No imputation will be performed for this analysis.
- For the second principal secondary endpoint, a treatment policy strategy (on and off treatment) analysis will be performed using an ANCOVA model including all participants with on and off treatment values, including factors for baseline score, treatment, and region. This will be done for both traditional and norm-based scoring. No imputation will be performed for this analysis.
- For the second principal secondary endpoint, a while alive and on treatment strategy (on treatment only) analysis will be performed using an ANCOVA model including all participants with on treatment values, excluding subjects who IP discontinue/rescue, including factors for baseline score, treatment, and region. This will be done for both traditional and norm-based scoring. No imputation will be performed for this analysis.

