- A Bayesian Hierarchical model will be defined using the above analysis model, where β_C is the parameter of interest. Both β_C and β_h are assumed to have $N(\mu, \tau^2)$, where τ^2 is the variance for the between-trial heterogeneity, which plays a key role in controlling the level of borrowing. As suggested in [Han, 2017], one appropriate form of prior for τ^2 is $\tau^{-2} \sim \Gamma(1, \epsilon)$. $\epsilon = 0.8$ will be used to allow the fair amount of variability between the historical control and the current control while preserving type I error. Details of the simulation settings and results are in a separate document.
- Other priors defined in the model are: $y_0 \sim N(\mu_0, \sigma_0^2)$, $y_i \sim N(\mu_i, \sigma_i^2)$, $\alpha_1, \alpha_2, \dots, \alpha_5, \mu_0, \mu_1 \sim N(0, 100)$, $\sigma_0^2, \sigma_1^2 \sim \Gamma(0.01, 0.01)$, $x_1 \sim N(\mu_1, \sigma_{x_1^2})$ where $\mu_1 \sim N(0, 100)$ and $\sigma_{x_1^2} \sim \Gamma(0.01, 0.01)$ for baseline SF-36 Vitality Sub-score.
- 10,000 burn in and 20,000 Bayesian iterations will be used.

Model Results Presentation

- For the SF-36 secondary endpoint, the Bayesian empirical mean and standard deviation of the change from baseline will be presented for each treatment arm (i.e. Placebo, Historical Placebo, and Dapro), the Bayesian empirical mean for β_C , will be presented along with one-sided p-value and 95% credible interval. The number of participants contributing to the analysis and the associated mean and standard deviation of the baseline and Week 28 SF-36 Vitality sub-score value will also be displayed with the results of the Bayesian model.
- SF-36 data will be summarized and analysed using both norm-based and traditional scoring, see Section 10.6.5 for details.

Model Results Interpretation

- One-sided p-values will be compared to 0.025 to assess nominal significance

CONFIDENTIAL

205270

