| 2.76. | ITT | EFF_T26 | Summary of Analysis of On-Treatment Observed and Imputed SF-36 Vitality Change from Baseline at Week 28, including external historical placebo dataset, Traditional Scoring | Traditional scoring On-Treatment Observed and Imputed | DR, SAC |
| 2.77. | ITT | EFF_T26 | Summary of Analysis of On-Treatment Observed and Imputed SF-36 Vitality Change from Baseline at Week 28, including external historical placebo dataset, Norm-based Scoring | Norm scoring On-Treatment Observed and Imputed | DR, SAC |
| Exploratory Efficacy Statistical Analyses: Hgb Variability | | | | | |
| 2.78. | ITT | EFF_T8 | Summary of Percentage of Time Hemoglobin is above or below the target range of 11 to 12 g/dL during the EP using Evaluable Hemoglobin Values | On-treatment | DR, SAC |

CONFIDENTIAL

205270

| Efficacy: Tables | | | | | |
|------------------|------------|----------------------|--|--|-------------|
| No. | Population | IDSL / Example Shell | Title | Programming Notes | Deliverable |
| 2.79. | ITT | EFF_T8 | Summary of Percentage of Time Hemoglobin is above or below the target range of 11 to 12 g/dL during the Treatment Period using Evaluable Hemoglobin Values | On-treatment | DR, SAC |
| 2.80. | ITT | EFF_T6 | Summary of Number of Subjects with mean Hemoglobin above, within, or below the Hemoglobin target range during the EP using Evaluable Hemoglobin Values | On-treatment | DR, SAC |
| 2.81. | ITT | EFF_T6 | Summary of Number of Subjects with mean Hemoglobin above, within, or below the Hemoglobin target range during the Treatment Period using Evaluable Hemoglobin Values | On-treatment | DR, SAC |
| 2.82. | ITT | EFF_T6 | Summary of Number of Subjects with a Hemoglobin <7.5 g/dL during the EP using Evaluable Hemoglobin Values | On-treatment Repeat for HemoCue Hgb and Central Laboratory Hgb | DR, SAC |
| 2.83. | ITT | EFF_T6 | Summary of Number of Subjects with a Hemoglobin <7.5 g/dL during the Treatment Period using Evaluable Hemoglobin Values | On-treatment Repeat for HemoCue Hgb and Central Laboratory Hgb | DR, SAC |
| 2.84. | ITT | EFF_T51 | Summary of Hemoglobin Increases Using Evaluable Hemoglobin Values | On-treatment Include overall at week 28 Repeat for HemoCue Hgb and Central Laboratory Hgb Similar to 204837 table 2.042 | DR, SAC |

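### One historical-borrowing prior is set in score points but used for both SF-36 vitality scorings, so the two planned tables fit different borrowing models to the same data

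*SAP*

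**What the plan says.** SAP 7.3.2.1 (Additional SF-36 Analyses) combines this trial with the TREAT placebo data in a Bayesian hierarchical model. The current and historical control effects share a normal distribution with variance tau². The SAP says of tau² that it is the between-trial heterogeneity, "which plays a key role in controlling the level of borrowing". The inverse of tau² has a Gamma(1, epsilon) prior with a single value, epsilon = 0.8, which "will be used to allow the fair amount of variability between the historical control and the current control while preserving type I error". The supporting simulations are in a separate document.

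The same section adds that "SF-36 data will be summarized and analysed using both norm-based and traditional scoring". The efficacy table list (SAP 10.10.6) carries this through. Table 2.76 is the borrowing analysis on the traditional score, and Table 2.77 is the same analysis "including external historical placebo dataset, Norm-based Scoring". The one-sided result is compared with 0.025 for nominal significance.

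SAP 7.2.5.2 gives the score limits applied to imputed values: "The low and high cutoffs at SF-36 values of 0 and 100 for traditional scoring and 22.89 and 70.42 for norm-based scoring". For the principal secondary vitality endpoint, that section treats traditional scoring as primary and norm-based as supportive. The borrowing section does not repeat the ranking. Nowhere does the SAP give a second epsilon, standardise the scores, name the scale on which 0.8 was tuned, or say whether the second Gamma parameter is a rate or a scale.

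**The concern.** Tau² is measured in squared score points, so a fixed prior on it means something different when the points change size. If the two scorings are linear transforms of each other, a reader will expect Tables 2.76 and 2.77 to show one result in two units. Under the rule as written they do not. The norm-based model allows more heterogeneity and so discounts the historical placebo arm more heavily. The estimate, the interval and the nominal significance call can all differ between the tables, for a reason unrelated to patients or treatment.

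**Working it through.** **Inputs from the documents.** Protocol 10.2.1 assumes "a between treatment effect of 5 points in favor of daprodustat and a within-group standard deviation of 21 points", with 540 evaluable participants, hence 270 per arm. The score limits are those in SAP 7.2.5.2, and the prior is the one in SAP 7.3.2.1.

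**Inputs assumed.** The two scorings are linearly related. The SD of 21 is on the 0-100 scale. The common mean of the two control effects has a flat prior, since its own prior is not clearly stated. The historical placebo number nH is not in the documents and is varied from 100 to 2000.

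**Step 1. Reproduce the plan's figure.** The SE of the difference is 21 × √(2/270) = 1.807. Power is Φ(5/1.807 − 1.96) = Φ(0.806) = 79%, as stated. The smallest significant difference is 1.96 × 1.807 = 3.54, against a stated 3.5. The SD and sample size are therefore read correctly.

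**Step 2. Scale factor (independent of nH).** k = (70.42 − 22.89)/100 = 0.4753.
- Ratio of allowed between-trial SDs in common units: 1/k = 2.10.
- Ratio of variances: 1/k² = 4.43.
- Reading Gamma's second parameter as a rate, the prior median of tau is √(0.8/ln 2) = 1.07 score points. On the traditional scale that is 1.07 points. On the norm-based scale it is 1.07/0.4753 = 2.26 traditional points.

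**Step 3. Weight on the historical arm.** Given tau, the historical mean receives weight

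W = (s²/270) / (s²/270 + s²/nH + 2·tau²)

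in the placebo estimate. W is averaged over the posterior of tau, with s = 21 (traditional) or 21 × 0.4753 = 9.98 (norm-based). With no conflict between the placebo groups, under the rate reading:

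| nH (assumed) | Traditional | Norm-based | Ratio |
|---|---|---|---|
| 100 | 0.191 | 0.120 | 1.6 |
| 300 | 0.314 | 0.169 | 1.9 |
| 500 | 0.363 | 0.185 | 2.0 |
| 1000 | 0.412 | 0.200 | 2.1 |
| 2000 | 0.442 | 0.208 | 2.1 |

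Across all scenarios run (rate or scale reading; conflict of 0, 2 or 5 points) the ratio lies between 1.6 and 2.4.

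**Step 4. Can the tables disagree?** Take an observed effect of 3 points in this trial and a historical placebo change 3 points lower than the current placebo. The estimate is then 3 + 3 × (mean weight). P(effect < 0) is the normal tail probability averaged over the posterior of tau (rate reading).

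| nH (assumed) | Scoring | Mean weight | Estimate (0-100 points) | P(effect < 0) |
|---|---|---|---|---|
| 300 | Traditional | 0.28 | 3.8 | 0.0136 |
| 300 | Norm-based | 0.15 | 3.4 | 0.0255 |
| 1000 | Traditional | 0.34 | 4.0 | 0.012 |
| 1000 | Norm-based | 0.17 | 3.5 | 0.024 |

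At nH = 300 the two results fall on opposite sides of 0.025. At nH = 1000 both are below it. Disagreement is possible but depends on the data.

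**Step 5. Does rescaling remove it?** Under the rate reading, norm-based scoring with epsilon = 0.8 × 0.4753² = 0.181 reproduces the traditional weights in every scenario (for example 0.314 at nH = 300 and 0.412 at nH = 1000). The scale dependence of the prior is therefore the whole explanation in this simplified model.

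**The case against.** The strongest reply is that little turns on this. The borrowing analysis was moved out of the principal endpoint (SAP 2.1, Table 1). It is exploratory and unadjusted under SAP 5.5, and its significance is nominal. Traditional scoring is the SAP's primary scoring for this domain, and the norm-based version borrows less, which is the cautious direction. All of this stands and limits the point to a correction of a secondary analysis. It does not make the two tables consistent, because a reader cannot tell a scale artefact from a genuine sensitivity result.

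A reader might also infer that the type I error statement cannot be true on both scales, or that it fails on the traditional scale. The documents support neither.
- **Both scales.** Norm-based scoring always borrows less at the same epsilon. If 0.8 was tuned on the traditional scale, control against adverse drift carries over to the norm-based scale. With no drift, simulated one-sided error is about 2% on both. Only tuning on norm-based scores alone would leave the traditional analysis borrowing more than was checked, and nothing says that happened.
- **Traditional scale.** Error does rise if the historical placebo response is lower. With 300 historical patients and 4 points of drift, the simulation gives 6.6% traditional and 3.8% norm-based. Both inputs are assumed, and some inflation under drift is usual with borrowing. The drift range and the meaning of preservation sit in a simulation document that is not available here, so this does not show the SAP's statement to be wrong.

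**Conclusion.** The inconsistency is real and follows from the SAP's own text: one unscaled prior, two scorings, two planned tables. Given linear conversion, the factors of 2.10 in SD and 4.43 in variance are exact. The size of the borrowing difference, about 1.6 to 2.4 times by weight, rests on 270 per arm, SD 21 on the 0-100 scale, a flat prior on the common mean and the assumed historical sample size. Describing it as exactly double would overstate what can be shown. Opposite nominal significance calls are possible, not certain. No conclusion in the testing hierarchy is affected, and the point says nothing against the type I error statement itself.

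**What to change.** **Preferred.** Fit the borrowing model once, on the traditional scale. Obtain Table 2.77 by multiplying the estimated effect and its credible limits by 0.4753; the probability is unchanged. First confirm the linear relation and the factor against the scored data. This costs one sentence in SAP 7.3.2.1 and removes one model run.

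**Alternative.** If both fits are wanted, state the scale on which 0.8 was calibrated and whether the second Gamma parameter is a rate or a scale. Then rescale epsilon for the other scoring:
- Calibrated on 0-100, rate: multiply by 0.226, giving 0.18 for norm-based scores.
- Calibrated on 0-100, scale: divide by 0.226, giving 3.54.
- Calibrated on norm-based scores: reverse the operation to obtain the 0-100 value.

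The other priors expressed in score units need the same treatment. The value 0.18 should not be adopted without settling the parameterisation. Under the scale reading with 1000 historical patients it would cut the norm-based weight from 15% to 4%, against 35% on the traditional scale, and so widen the gap.

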7.4. Exploratory Efficacy Analyses

No statistical testing is planned for exploratory endpoints.

7.4.1. Endpoint / Variables

| Exploratory | |
|--|--|
| Objectives | Endpoints |
| 
 Further evaluations to compare daprodustat to placebo on Hgb variability | 
 % of time Hgb is above or below range. Number (%) of participants with mean Hgb above and below range. Number (%) of participants with a Hgb < 7.5 g/dL Number (%) of participants with a > 2 g/dL increase in Hgb within any 4 week period up to EP N (%) of participants with a Hgb value \geq 13 g/dL during the treatment period Number of times Hgb \geq 13 g/dL during the treatment period % of time Hgb \geq 13 g/dL during the treatment period. |
| 
 Further evaluation to compare daprodustat to placebo on Hgb change. | 
 % of participants who achieved a Hgb increase of \geq 1.0g/dL % of time Hgb increase of \geq 1.0 g/dL from baseline % of participant having a Hgb increase of \geq 1.0 g/dL at each post-baseline visit. % of participants who achieved and maintained a Hgb increase of \geq 1.0g/dL between baseline and EP. |
| 
 To compare daprodustat to placebo on measures of iron status and use | 
 Observed change from baseline in hepcidin, ferritin, transferrin saturation, serum iron, total iron binding capacity (TIBC) Average monthly oral iron dose/participant (mg) to Week 28 N (%) of participants who reduced oral iron supplementation from baseline N (%) of participants requiring IV iron each month. Average monthly IV iron dose/participant (mg) to Week 28 Time to first IV iron use, rhEPO and transfusion use |

CONFIDENTIAL

205270

| Exploratory | |
|--|---|
| Objectives | Endpoints |
| | 
 Summary of frequency and dose of IV iron use, rhEPO and transfusion use |
| 
 To compare daprodustat to placebo on renal function | 
 Estimated Glomerular Filtration Rate (eGFR) observed and change from baseline Serum creatinine observed and change from baseline N (%) transitioning to dialysis |
| 
 Evaluate the dose adjustment schemes | 
 Assigned dose by visit Most recent dose prior to Week 24, Week 28 and End of Treatment Maximum achieved dose Number (%) of participants with 0, 1, 2 or >2 dose adjustment Mean number of dose adjustments Time dose held for Hgb \geq 13 g/dL |
| 
 To compare daprodustat to placebo on BP medication changes | 
 N (%) of subjects who had no change, an increase or a decrease in the number of BP medications from baseline to week 28 or final visit for non-completers |
| 
 To compare daprodustat to placebo on the severity and change in symptoms | 
 N(%) of participants within each PGI-C symptom change. |
| 
 To compare daprodustat to placebo for improving physical activity (actigraphy) | 
 Change in percent and mean number of hours of daily activity from baseline. Change in percent sleep efficiency from baseline. |

7.4.2. Planned Exploratory Efficacy Display Details

Hgb Variability

All exploratory Hgb endpoints include those participants on treatment only.

| Endpoint/Variables |
|--|
| 
 % of time Hgb is above or below the target range of 11 to 12 g/dL during the EP and during the treatment period Number (%) of participants with mean Hgb above, within, and below the Hgb target range during the EP and during the treatment period Number (%) of participants with a Hgb <7.5 g/dL during the EP and during the treatment period Number (%) of participants with a >2 g/dL increase in Hgb within any 4-week period up to and including the EP N (%) of participants with a Hgb value \geq 13g/dL during the treatment period |

CONFIDENTIAL

205270

- Number of times Hgb \geq 13 g/dL during the treatment period
- % of time Hgb \geq 13 g/dL during the treatment period
- N (%) of participants who achieved a Hgb increase of \geq 1.0g/dL during the EP
- % of time Hgb increase of \geq 1.0 g/dL from baseline during the treatment period
- N (%) of participant having a Hgb increase of \geq 1.0 g/dL at each post-baseline visit.
- N (%) of participants who achieved and maintained a Hgb increase of \geq 1.0g/dL between baseline and EP

Planned Exploratory Displays

- The % time Hgb is above or below the Hgb target range (11-12 g/dL) during the EP and during the treatment period will be summarized using mean, standard deviation, minimum, P25, median, P75, and maximum by treatment group. This summary will be presented using evaluable Hgb values only (see Section 10.6.3).
- Number (%) of participants with mean Hgb above, within and below the Hgb target range during the EP and during the treatment period will be summarized by treatment group. This summary will be presented using evaluable Hgb values only (see Section 10.6.3)
- The number and percentage of participants with a Hgb value $<$ 7.5g/dL during the EP and during the treatment period will be summarized by treatment group using central laboratory Hgb values and separately using HemoCue Hgb values. This summary will be presented using evaluable Hgb values only (see Section 10.6.3).
- The number and percentage of participants with a $>$ 2 g/dL increase in Hgb within any 4-week period up to and including the EP will be summarized by visit up to Week 28 and overall at Week 28 by treatment group using central laboratory Hgb values and separately using HemoCue Hgb values. This summary will be presented using evaluable Hgb values only (see Section 10.6.3).
- The number and percentage of participants with a Hgb value \geq 13 g/dL and the number of times a Hgb value \geq 13 g/dL occurs during the treatment period will be summarized by treatment group using central laboratory Hgb values and separately using HemoCue Hgb values. This summary will be presented using evaluable Hgb values only (see Section 10.6.3).
- The percentage of time Hgb is \geq 13 g/dL during the treatment period will be calculated using the Rosendaal method [Rosendaal, 1993]. The percentage of time Hgb is \geq 13 g/dL during the treatment period will be summarized using mean, standard deviation, minimum, P25, median, P75, and maximum by treatment group. This summary will be presented using evaluable Hgb values only (see Section 10.6.3).
- The number and percentage of participants who achieved a Hgb increase of \geq 1.0g/dL during the EP will be summarized by treatment group using central laboratory Hgb values and separately using HemoCue Hgb values. This summary will be presented using evaluable Hgb values only (see Section 10.6.3).
- The percentage of time Hgb increase of \geq 1.0 g/dL from baseline during the treatment period will be calculated using the Rosendaal method [Rosendaal, 1993]. The percentage of time Hgb increase of \geq 1.0 g/dL from baseline during the treatment period will be summarized using mean, standard deviation, minimum, P25, median, P75, and maximum by treatment group. This summary will be presented using evaluable Hgb values only (see Section 10.6.3).
- The number and percentage of participants who have a Hgb increase of \geq 1.0 g/dL at each post-baseline visit will be summarized by treatment group using central laboratory Hgb values and separately using HemoCue Hgb values. This summary will be presented using evaluable Hgb values only (see Section 10.6.3).

CONFIDENTIAL

205270

- The number and percentage of participants who achieved and maintained a Hgb increase of ≥ 1.0 g/dL between baseline and EP will be summarized by treatment group using central laboratory Hgb values and separately using HemoCue Hgb values. To be considered as maintaining Hgb increase ≥ 1.0 g/dL, must have both Week 24 and Week 28 CFB ≥ 1.0 g/dL. This summary will be presented using evaluable Hgb values only (see Section 10.6.3).

Iron Parameters

| Endpoint / Variables |
|--|
| 
 • Observed change from baseline in hepcidin, ferritin, transferrin saturation (TSAT), serum iron, total iron binding capacity (TIBC) across all visits • Average monthly oral iron dose/participant (mg) to Week 28 • N (%) of participants who reduced oral iron supplementation relative to baseline [defined as total oral iron (mg) over 4 weeks prior to randomization] during EP [defined as average monthly oral iron dose (mg) over Weeks 24 to 28] and during the treatment period • N (%) of participants requiring IV iron each month. • Average monthly IV iron dose/participant (mg) to Week 28 • Time to first IV iron use, rhEPO and transfusion use • Summary of frequency and dose of IV iron use, rhEPO and transfusion use |
| Planned Exploratory Displays |
| 
 • Hepcidin, ferritin, and serum iron on-treatment values will be log-transformed (see Section 5.2.2) and summarized using geometric mean, coefficient of variation, minimum, P25, median, P75, and maximum for each scheduled visit by treatment group. Graphical summaries will be provided. • TSAT and TIBC on-treatment values will be summarized using mean, standard deviation, minimum, P25, median, P75, and maximum for each scheduled visit by treatment group. Graphical summaries will be provided. • Percent change from baseline in log-transformed (see Section 5.2.2) hepcidin, ferritin, and serum iron on-treatment values will be summarized using geometric mean, coefficient of variation, minimum, P25, median, P75, and maximum for each scheduled visit by treatment group. Graphical summaries will be provided. • Change from baseline in TSAT and TIBC on-treatment values will be summarized using mean, standard deviation, minimum, P25, median, P75, and maximum for each scheduled visit by treatment group. Graphical summaries will be provided. • Average monthly oral or IV iron dose (mg)/participant to Week 28 will be determined by calculating the total elemental oral or IV iron dose per participant from Day 1 to Week 28 while the participant was on randomized treatment and dividing by (the number of days the participant was on randomized treatment/30.4375 days). (see Section 10.6.3) • Average monthly oral iron dose/participant and average monthly IV iron dose/participant at baseline, and while on treatment to Week 28 will be summarized by treatment group (see Section 10.6.3). Summaries will include mean, standard deviation, minimum, P25, median, |

CONFIDENTIAL

205270

P75, and maximum by treatment group.

- The number and percentage of participants that reduced oral iron supplementation relative to baseline during the EP and during the treatment period while on treatment will be summarized by treatment group (see Section 10.6.3).
- The number and percentage of participants who required IV iron during study treatment (day 1 to week 28) will be summarized by treatment group.
- Time to first IV iron use, rhEPO and transfusion use is defined as the time from Randomization until the date on which a participant received IV iron, rhEPO, or transfusion use for the first time after Randomization. Time to first IV iron use will use on-treatment values only, while time to first rhEPO and transfusion use will use both on-treatment and on/off-treatment values post-randomization. First rhEPO use differs from rescue, there may be instances of rhEPO being given but participants not rescued. The Number (%) of participant received IV iron, rhEPO and transfusion use within each treatment arm will be summarised with mean, standard deviation, minimum, P25, median, P75, and maximum of the time to first IV, rhEPO and transfusion use by treatment group.
- The frequency and dose of IV iron use, rhEPO and transfusion use will be summarized using mean, standard deviation, minimum, P25, median, P75, and maximum by treatment group.
- A listing of all IV iron use, rhEPO and transfusion use during the study will be provided. This listing will include treatment, site ID, unique subject ID, select demographic information, frequency and dose of IV iron use, frequency and dose of rhEPO use, and frequency of transfusions.

Renal Function

| Endpoint / Variables |
|---|
| 
 • Estimated Glomerular Filtration Rate (eGFR) observed and change from baseline • Serum creatinine observed and change from baseline • N (%) transitioning to dialysis |
| Planned Exploratory Displays |
| 
 • eGFR and serum creatinine on-treatment values will be summarized using mean, standard deviation, minimum, P25, median, P75, and maximum for each scheduled visit by treatment group. Graphical summaries will be provided. • Change from baseline in eGFR and serum creatinine on-treatment values will be summarized using mean, standard deviation, minimum, P25, median, P75, and maximum for each scheduled visit by treatment group and by subgroup ADPKD. Graphical summaries will be provided. • Number (%) of participants transitioning to dialysis will be summarized by treatment group. |

CONFIDENTIAL

205270

Dose Adjustment Scheme

| Endpoint / Variables |
|---|
| 
 • Assigned dose by visit • Most recent dose prior to Week 24, Week 28 and end of study treatment • Maximum achieved dose • Number (%) of participants with 0, 1, 2, or >2 dose adjustments during the treatment period • Mean and median number of dose adjustments during the treatment period • Time dose held for Hgb ≥ 13 g/dL during the treatment period |
| Planned Exploratory Displays |
| 
 • The assigned dose by visit will be summarized using mean, standard deviation, minimum, P25, median, P75, and maximum. • The most recent dose prior to Week 28 and end of treatment will be summarized by the number and percentage of participants at each dose level. • The maximum achieved dose will be summarized using mean, standard deviation, minimum, P25, median, P75, and maximum. • The number and percentage of participants with 0, 1, 2, or >2 dose adjustments will be summarized by treatment group during the treatment period. This summary will be produced twice – the first time counting all dose adjustments, including adjustments related to periods of dose holds (i.e., no study treatment is given), the second time excluding dose adjustments related to periods of dose hold. • The time (in days) that study treatment was withheld for Hgb values ≥ 13 g/dL per participant will be summarized using mean, standard deviation, minimum, P25, median, P75, and maximum during the treatment period. |

Blood Pressure

| Endpoint / Variables |
|--|
| 
 • N (%) of subjects who had no change, an increase or a decrease in the number of BP medications from baseline to week 28 or final visit for non-completers |
| Planned Exploratory Displays |
| 
 • Summary table listing the N (%) of subjects in each treatment group who have no change, an increase or a decrease in the number of BP medications from baseline to week 28 or final visit for non-completers. Summary to include: 
 ○ For subjects who have no change in the number and class of blood pressure medications taken between baseline and Week 28. ○ For subjects who have the same number of blood pressure medications taken at baseline and Week 28, but a change in the class ○ For subjects who have an increase in the number of blood pressure medications taken between baseline and Week 28 ○ For subjects who have a decrease in the number of blood pressure medications taken |

CONFIDENTIAL

205270

between baseline and Week 28

- If a subject has an increase and then a decrease (or vice versa) in the number of blood pressure medications taken, for reporting purposes that subject will be categorized as having an increase in the number of medications and they will appear in the increase table above.

Severity and Change in Symptoms

| |
|--|
| Endpoint / Variables |
| 
 • N(%) of participants within each PGI-C symptom change. |
| Planned Exploratory Displays |
| 
 • Scoring for the PGI-S is outlined in Section 10.6.5. The number and percentage of participants in each PGI-C category at each scheduled on treatment visit will be summarized. |

Physical Activity (Actigraphy)

| |
|---|
| Endpoint / Variables |
| 
 • Change in percent and mean number of hours of daily activity from baseline. • Change in percent sleep efficiency from baseline. • Wear time of actigraphy device |
| Planned Exploratory Displays |
| 
 • The on treatment percentage of daily light, moderate, vigorous, very vigorous, and moderate to vigorous physical activity (MVPA) activity at each Actigraphy collection period will be defined as the average percentage of daily light, moderate, vigorous, very vigorous, and MVPA activity during the collection period. • The on treatment mean number of hours of daily light, moderate, vigorous, very vigorous, and MVPA activity at each Actigraphy collection period will be calculated as the average number of hours of daily light, moderate, vigorous, very vigorous, and MVPA activity during the collection period. • The on treatment percentage and mean number of daily light, moderate, vigorous, very vigorous, and MVPA activity, the percent sleep efficiency, and wear time will be summarized using mean, standard deviation, minimum, P25, median, P75, and maximum by treatment group at all Actigraphy collection periods. • Change from baseline in the on treatment percentage and mean number of daily light, moderate, vigorous, very vigorous, and MVPA activity, the percent sleep efficiency, and wear time will be summarized using mean, standard deviation, minimum, P25, median, P75, and maximum by treatment group at all Actigraphy collection periods. |

